10.2 Statistical Hypotheses

- 1) BCI will be feasible and safe, with a maximum tolerated dose to be determined in this trial.
- 2) Post-BCI peripheral blood will demonstrate an increase in the percent of CD8⁺ T cells expressing a combination of Ki67⁺, PD-1+, HLA-DR⁺, CD38⁺, and Bcl-2^{low} compared to pre-BCI peripheral blood CD8⁺ T cells.
- 3) CD8+ T cell responses to BCI will be greater among subjects with high PD-1 expressing T cells in BAL effluent.

10.3 Analysis Datasets

All participants who were treated with BCI will be included.

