| Brief Summary | This is a first-in-human, safety and feasibility study of bronchoscopic cryo- immunotherapy (BCI) of peripheral lung tumors in advanced non-small cell lung cancer (NSCLC) and suspected NSCLC. BCI has the potential to stimulate anti-tumor immune responses. Pre- and post-BCI peripheral blood samples will be analyzed to assess for anti-tumor immune responses. Post- BCI peripheral blood will be collected 7 and 14 days after the procedure. Additionally, pre-BCI bronchoalveolar lavage (BAL) specimens will be collected to correlate PD-1 phenotype on pre-BCI BAL lymphocytes by single cell RNA sequencing and BCI-induced anti-tumor immune responses. | | |
| Phase | Phase I | | |
| Objectives Primary: • Establish safety and feasibility of BCI and determine the maximu tolerated dose (MTD) (i.e., freeze duration) Secondary: | | | |
| Assess the extent of BCI-induced anti-tumor immune respons | | | |
| Methodology Dose-escalation trial using a 3+3 design Primary: Feasibility and Safety | | | |
| | Feasibility: successful performance of BCI in at least 80% of participants in whom BCI is attempted Safety endpoints: Dose-limiting toxicity (DLT), defined as incidence of bleeding complications and pneumothorax, length of time to perform BCI, length of fluoroscopy exposure during BCI, and other adverse events | | |
| Endpoints | Secondary: Immune Analysis and Tumor Response Changes in peripheral blood CD8⁺ T cells expressing a combination of Ki67⁺,PD-1+, HLA-DR⁺, CD38⁺, and Bcl-2^{low} after BCI Changes in peripheral blood lymphocyte gene expression after BCI, which will be assessed by the PanCancer OncolmmuneTM profile panel, a 770-plex gene expression panel covering innate and adaptive immune responses (NanoString® Technology, Seattle, WA) Correlation of PD-1 phenotype of pre-BCI BAL lymphocytes by single-cell RNA sequencing and BCI-induced anti-tumor immune responses. | | |
| Study Duration 12 months | | | |
| Participant Duration | 14 days | | |
| Duration of IP administration | BCI will be performed once at the time of a standard-of-care bronchoscopy for another indication. BCI is anticipated to take approximately 15-25 minutes. | | |

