If the patient does not have biopsy-proven non-small cell lung cancer prior to the procedure, the clinical team will obtain diagnostic biopsies per standard protocol without input from researchers. Exact location and type of biopsies (i.e. transbronchial needle aspiration of mediastinal or hilar lymph nodes and/or transbronchial biopsies of peripheral tumor) will be determined by the clinical team. The transbronchial biopsies will be prepared for frozen section and/or transbronchial needle aspirates for rapid on-site cytology evaluation (ROSE), as indicated. If ROSE is performed a certified cytotechnologist will perform a rapid microscopic analysis of the ROSE specimen to confirm presence or absence of malignant cells. In cases where non-small lung cancer cannot be confirmed, but it is highly suspected based on clinical criteria, ROSE or frozen section, select patients with high-risk features for NSCLC, including significant smoking history, history of COPD, spiculated lesion with bronchus sign on chest CT, enlarged of mediastinal/hilar lymph nodes and or distant metastatic disease on chest CT or PET CT scan, may be enrolled.

Description of BCI:

In BCI, a radial endobronchial ultrasound (EBUS) probe (Olympus Ultrasonic Probe UM-S20-17S or UM-S20-20R, Tokyo, Japan) with a flexible guide sheath will be inserted into the working channel of a flexible bronchoscope, or may be inserted through the working channel of a robotic bronchoscope, and advanced into the target bronchial sub-segment to identify the peripheral tumor. If the peripheral tumor is unable to be identified by radial ultrasound within twenty minutes, then the patient will not be a candidate to undergo BCI. Once the peripheral tumor is identified by radial EBUS

CONFIDENTIAL

probe will be removed, but the guide sheath will remain in position to serve as a position marker and as a conduit from the bronchoscope to the location of peripheral tumor, if robotic bronchoscopy is being performed, the bronchoscope itself serves as the guide sheath. This will be performed under fluoroscopic guidance to confirm stability of guide sheath or robotic bronchoscopy position.

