2.3 Potential Risks & Benefits

2.3.1 Known Potential Risks

Potential Risks of Bronchoscopic Cryo-Immunotherapy (BCI)

The radial endobronchial ultrasound probe, which will be used to identify lung tumors in BCI, could potentially cause airway trauma, bleeding, or pneumothorax in rare cases. When lung tumors undergo cryoablation in BCI, potential risks include bleeding, hemoptysis, and pneumothorax. Because BCI does not involve taking any biopsies or removing any lung tissue, the risk of bleeding, hemoptysis, and pneumothorax directly related to this intervention are anticipated to be low. After applying freezing temperatures, rewarming will occur to ensure that the cryoprobe does not remain frozen to the target lung tumor. This will avoid accidentally removing or performing a biopsy on the target tumor, which could cause bleeding, hemoptysis, or pneumothorax. However, if a large pneumothorax occurs and is not properly treated, or if severe bleeding occurs, which is not properly controlled, then these potential complications could theoretically cause severe hypoxemia and be life-threatening. If a pneumothorax occurs, treatment with oxygen and possibly tube thoracostomy, depending on the size of the pneumothorax, will be provided. If significant bleeding or hemoptysis occurs, treatment to stop the bleeding may include applying iced saline, topical epinephrine, or placement of an endobronchial blocker. There may be additional risks of BCI that are currently unforeseeable. We will take all due precautions to determine if a potential participant is at increased risk for any adverse events and to minimize any potential complications in advance of undergoing BCI.

BCI will involve exposure to radiation from fluoroscopy to guide the placement of the probe. The risks of receiving very small doses of radiation are thought to be low. These risks are not actually known. Pregnant women cannot be exposed to radiation. Women of child-bearing age must have a negative pregnancy test before they can have an X-ray and undergo appropriate lead shielding to minimize exposure to reproductive organs.

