3.1 Primary Objective: Demonstrate Feasibility and Determine the MTD

1) Demonstrate feasibility of BCI

We hypothesize that BCI will be feasible, defined as successful performance in at least 80% of patients in whom BCI is attempted. Successful performance of BCI will require identification of the target peripheral lung tumor by radial endobronchial ultrasound within 20 minutes followed by completed cryoablation of target tumor.

2) Determine the safety and MTD of BCI

We hypothesize that BCI will prove safe at each planned dose level. Using a standard 3+3 design, the trial will determine the maximally tolerated dose (MTD) by sequentially assessing increasing freeze times during the procedure. Dose-limiting toxicity (DLT) is defined as the occurrence of any of the following: grade 2 or 3 bleeding, pneumothorax necessitating tube thoracostomy, or any NCI CTCAE grade 4 or 5 adverse events, which may be possibly, probably, or definitely related to BCI (33). The monitoring period for dose limiting toxicity will be for seven days post-BCI.

3.2 Secondary Objectives: Assess BCI Induced Anti-Tumor Immune Responses1) Pre- and Post-BCI Peripheral Blood Analysis

We hypothesize that BCI will induce activation and proliferation of peripheral blood T cells. Based on previous work (26, 27) (see section 2.1.IV for full details), we hypothesize that some combination of the following markers will be displayed on peripheral blood CD8⁺ T cells after BCI: HLA-DR and CD38 (surface markers of CD8⁺ T cell activation), Ki-67 (a cell cycle marker of proliferation), Bcl-2 (an anti-apoptotic protein downregulated on activated CD8⁺ T cells), and PD-1. We also hypothesize that there will be significant changes in peripheral blood lymphocyte gene expression after BCI, which will be assessed by the PanCancer OncoImmune[™] profile panel, a 770-plex gene expression panel covering innate and adaptive immune responses (NanoString® Technology, Seattle, WA).

2) Investigate BCI Association with PD-1 Phenotype of Effector T cells in NSCLC

We hypothesize that BCI will induce PD-1 phenotype in circulating effector T cells on single-cell RNA sequence analysis and that CD8+ T cell responses to BCI will be greater among subjects with high PD1 expressing T cells in BAL effluent.

4 Study Design and Endpoints

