4.2 Study Endpoints

4.2.1 Primary Study Endpoints: Feasibility and Safety

- Each patient will be classified as having successfully undergone BCI or not. Feasibility of BCI is defined as successfully performing BCI in at least 80% of patients in whom BCI is attempted. Successful performance of BCI will require identification of the target peripheral lung tumor by radial endobronchial ultrasound within 20 minutes followed by completed cryoablation of target tumor. The target tumor will have freeze-thaw cycles applied every one centimeter of the largest diameter. Additional BCI features will be described as follows:
 - a) Ability of radial endobronchial ultrasound to identify peripheral lung tumor
 - b) Length of time to perform BCI
 - c) Length of time of fluoroscopy exposure during BCI
- 2) Dose-limiting toxicities (DLT) will be used to guide the dose-escalation procedure and determine the maximum tolerated dose. A DLT is defined as any of the following occurring up to 7 days post-BCI:
 - Grade 2 or 3 bleeding, based on the following scale (34):
 - a) Grade 0: absence of bleeding
 - b) Grade 1: bleeding requiring suctioning to clear
 - c) Grade 2: bleeding requiring an endoscopic procedure (iced saline, 1:20,000 topical epinephrine, or bronchial occlusion)
 - d) Grade 3: severe bleeding (>100cc total volume). Severe bleeding will also be defined as bleeding which cannot be controlled endoscopically, requires ICU admission or interventional radiology/ surgical intervention, or results in respiratory or hemodynamic instability (34)
 - Pneumothorax necessitating tube thoracostomy; recorded features of pneumothorax to include:
 - a) size
 - b) associated symptomatology
 - c) respiratory impairment
 - d) need for chest tube placement
 - Any NCI CTCAE (33) grade 3, 4, or 5 adverse events, which may be possibly, probably, or definitely related to BCI

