10.4.2 Analysis of the Primary Endpoint: Feasibility

The proportion of patients in whom BCI is successfully completed will be estimated, along with its 95% exact confidence interval.

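### The feasibility denominator in 4.2.1 (BCI attempted) is not carried into 10.3 or 10.4.2, and using the treated set would drop every failure to find the tumor

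*Combined protocol and SAP*

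**What the plan says.** Feasibility is a primary endpoint. Section 4.2.1 states: "Feasibility of BCI is defined as successfully performing BCI in at least 80% of patients in whom BCI is attempted". The protocol summary has the same criterion ("successful performance of BCI in at least 80% of participants in whom BCI is attempted"), and 3.1 repeats it as the hypothesis. Sections 3.1 and 4.2.1 both make success a two-part event: "identification of the target peripheral lung tumor by radial endobronchial ultrasound within 20 minutes followed by completed cryoablation of target tumor". Section 4.2.1 also lists, as a descriptive feature (item a), "Ability of radial endobronchial ultrasound to identify peripheral lung tumor".

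The analysis sections are shorter. Section 10.3 contains one sentence: "All participants who were treated with BCI will be included". Section 10.4.2 contains one sentence: "The proportion of patients in whom BCI is successfully completed will be estimated, along with its 95% exact confidence interval". Neither refers back to 4.2.1, and no section defines what counts as an attempt.

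Sections 2.2 and 6.1.3 say that a patient whose tumor is not found by radial ultrasound within 20 minutes is no longer a candidate, and 7.1.2 says that BCI is then not done. Section 5.1 makes EBUS visualization at bronchoscopy an inclusion condition. On the other hand, the description in 2.2 begins "In BCI, a radial endobronchial ultrasound (EBUS) probe", and 2.3.1 speaks of "The radial endobronchial ultrasound probe, which will be used to identify lung tumors in BCI". Both treat the ultrasound search as part of BCI.

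**The concern.** The endpoint section and the analysis section point to different denominators. Under 4.2.1 a patient can fail in two ways: the tumor is not found in time, or it is found but cryoablation is not completed. A patient who fails in the first way receives no BCI and so is outside the set in 10.3. If the analyst applies 10.3 to feasibility, the identification half of the success definition is met by construction, and only incomplete cryoablation can count against the procedure. The proportion and its exact interval then estimate completion given identification. That is a legitimate quantity, but it is not feasibility as 4.2.1 defines it.

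At stake is whether a primary endpoint is reported as meeting its 80% criterion. The same data can meet or miss it depending on which section is followed.

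**Working it through.** **Inputs.** The 80% criterion and the two-part success definition come from 3.1 and 4.2.1. The planned size is 15-24 in 5.6, up to 24 in the summary and approximately 24 in 10.5. None of these says whether the number counts attempted or treated patients, so both are worked below. The plan gives no power or precision figure for feasibility, so there is none to reproduce.

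The one detection rate in the documents is from the cryobiopsy study described in 2.1 (III): 31 lesions found among 38 subjects, or 37 if the excluded subject is subtracted from the 38, with all 31 completed. The other detection rates, 90% and 95%, are assumptions.

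**Assumption throughout.** Every identified tumor is fully cryoablated, so the treated-set estimate is always 100%.

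**Step 1: how many non-identifications f miss 80% on the 4.2.1 denominator.**

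- 24 attempted: (24 − f)/24 < 0.80 requires f > 4.8, so f = 5.
- 24 treated, failures on top: 24/(24 + f) < 0.80 requires f > 6, so f = 7.
- 15 attempted: (15 − f)/15 < 0.80 requires f > 3, so f = 4.
- 15 treated: 15/(15 + f) < 0.80 requires f > 3.75, so f = 4.

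**Step 2: the two estimates at those counts (exact Clopper-Pearson 95% CI).**

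| Case | Attempted denominator | Treated set (10.3) |
|---|---|---|
| 24 attempted, 5 not found | 19/24 = 79.2% (57.8-92.9) | 19/19 = 100% (82.4-100) |
| 24 treated, 7 more not found | 24/31 = 77.4% (58.9-90.4) | 24/24 = 100% (85.8-100) |
| 15 attempted, 4 not found | 11/15 = 73.3% (44.9-92.2) | 11/11 = 100% (71.5-100) |
| 15 treated, 4 more not found | 15/19 = 78.9% (54.4-93.9) | 15/15 = 100% (78.2-100) |

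**Step 3: how likely the split is at detection rate p.** With N attempted, the number not found is binomial (N, 1 − p). The probability needed is P(at least 5) for N = 24 or P(at least 4) for N = 15. With m treated, enrollment continues until m tumors have been found, and the number not found is negative binomial. The probability needed is P(at least 7) for m = 24, which equals P(at most 23 found in the first 30 attempts), or P(at least 4) for m = 15.

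| Detection rate p | 24 attempted | 24 treated | 15 attempted | 15 treated |
|---|---|---|---|---|
| 81.6% (31/38) | 46% | 31% | 29% | 43% |
| 90% | 8.5% | 2.6% | 5.6% | 9.8% |
| 95% | 0.6% | 0.1% | 0.5% | 1.1% |

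**Step 4: the cited study on each denominator.** 31/31 = 100% (88.8-100); 31/37 = 83.8% (68.0-93.8); 31/38 = 81.6% (65.7-92.3). The denominators differ by 16 to 18 percentage points, but all three estimates meet 80%.

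**The case against.** The strongest reply is that the denominator is already specified. The summary, 3.1 and 4.2.1 all give it, and 10.4.2 is headed as the analysis of that endpoint. A specific definition stated three times would normally govern over one general sentence in 10.3, which does not say that only treated participants are included. This much stands: a reader might infer that the plan gives no feasibility denominator, or that identification failures will certainly be dropped, and the documents support neither. What remains is that attempted is undefined, 10.3 names no other set and makes no exception for feasibility, and 10.4.2 does not refer back.

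A second reply is that an unidentified tumor is a screen failure found during the procedure. The inclusion condition in 5.1 and the candidacy wording in 2.2 and 6.1.3 allow that reading. But the 20-minute requirement in the success definition would then do no work, because nobody in the denominator could fail it. The reading also fits poorly with 2.2 and 2.3.1, which place the ultrasound search within BCI.

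A third reply is that item (a) of 4.2.1 reports identification anyway. That helps a reader rebuild the other proportion, provided the item is not itself restricted to treated patients. It does not say which proportion is judged against 80%.

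Two limits on size are fair. The bronchus-sign requirement in 5.1 may raise detection above the cited study's rate, and at 90-95% the probabilities are small. Section 10.4.2 plans an estimate with an interval and no test, and the intervals are wide on either denominator.

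**Conclusion.** Section 10.3, if used for feasibility, is wrong as written. It contradicts the 4.2.1 definition and biases the estimate upward by removing every identification failure. The estimate is not forced to 100%, because treated patients with incomplete cryoablation still count as failures. The 100% figures above follow from the assumption that every identified tumor is completed.

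The size depends on two unknowns: this trial's detection rate, and whether planned numbers count attempted or treated patients. Near the cited study's 81.6%, the chance that the two denominators fall on opposite sides of 80% is 46% with 24 attempted and 31% with 24 treated. At 95% detection it is below 1% in both cases. A reader might infer from the cited study that the choice of denominator would reverse its conclusion; it would not, since that study meets 80% on every denominator.

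The 80% criterion does not enter the escalation rules (6.1.2) or the halting rules (8.4). The harm is confined to the reported feasibility conclusion. It should be fixed before analysis, because the choice of denominator should not be made after the counts are known.

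**What to change.** - In 4.2.1, define attempted: consented, otherwise eligible participants in whom the radial EBUS search for BCI was started.
- In 10.3, name this as the feasibility set. In 10.4.2, name it as the denominator, with non-identification within 20 minutes and incomplete cryoablation both counted as failures. Use the same set for item (a) of 4.2.1.
- Also report completion among identified tumors, so that both quantities are visible.
- Keep the treated set for the DLT and immune analyses.
- State whether the participant numbers in the summary, 5.6 and 10.5 count attempted or treated patients.

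The cost is a few sentences in 4.2.1, 10.3 and 10.4.2 and a clarifying phrase on numbers. Identification is already a described item, so no new type of data is needed. No procedural, eligibility or dose rule changes, and the clinical wording in 5.1, 2.2 and 6.1.3 can stay as it is. The downside for the sponsor is a possibly less favorable feasibility figure.

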10.4 Description of Statistical Methods

10.4.1 General Approach

- Continuous data will be summarized with means and standard deviations.
- Categorical data will be summarized with frequencies and percentages.
- *P* values will be considered statistically significant at the 0.05 level. Note that the study is designed to determine the MTD, and thus is not powered to detect statistically significant differences in any of the secondary outcomes.

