mRNA analysis: We will also be assessing a variety of other immune biomarkers from peripheral blood utilizing the NanoString[™] platform, including cytokine gene expression, that may allow for the establishment of a variety of peripheral blood biomarkers to correlate with the effects of BCI in advanced NSCLC. Once sorted, the CD8+ and CD4+CD25- cells (non-Treg cells) will be processed for RNA extraction and NanoString[™] mRNA quantitation. RNA extraction will be performed using the MARIS technique to insure RNA quality after sorting (35). We are particularly interested in determining gene expression of proteins involved in T cell activation and immune regulation, such as CTLA-4, PD-1, OX-40, TIM-3, IL-10, TGF-ß, IL-2, MHC-II and TNF-α. The transcriptome data will be processed in collaboration with the Biostatistics Division led by [name] at the NYU School of Medicine to calculate the relative expression of the key genes of interest previously noted. The NanoString[™] platform offers the convenience of straightforward high-throughput mRNA quantitation using RNA barcodes to probe and count mRNA transcripts of interest (28). Our preliminary analysis will be conducted with the pre-designed Oncolmmune[™] Profile panel, which measures 770 gene targets most relevant in tumor immunobiology.

2) Investigate BCI Association with PD1 phenotype of Effector T cells in NSCLC

Research Samples: In addition to peripheral blood specimens as described previously, BAL fluid will be collected from regions of the primary tumor and of the distal portion of the same lung.

Using a subset of samples from enrolled subjects enrolled with sufficient BAL specimens, we will perform single-cell RNA sequencing on sorted CD3+ T cells from BAL and PBMCs obtained at the time of BCI. This approach will be repeated in PBMC after 7 and 14 days post BCI. The percentage of PD-1 expressing T lymphocytes will be determined in CD4⁺ and CD8⁺ cells from both BAL and PBMC compartments. PD1⁺ cell percentage and transcriptome will be compared between responder categories. RNA sequencing and subsequent data analysis will be performed in the Genomic Technology and Bioinformatics Cores of NYU School of Medicine.

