7.1 Study Procedures/Evaluations

7.1.1 Study Specific Procedures

- Bronchoalveolar lavage from regions of the primary tumor and from the distal portion of the same lung on day 0
- BCI on day 0
- Blood draws on day 0 (prior to BCI) and on days 7 and 14 (± 3 days) (post-BCI)

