10.1 Statistical and Analytical Plans

All dose-limiting toxicities will be tabulated by type of DLT and dose level.

In addition to tabulating toxicities, we will record data on pre- and post-BCI peripheral blood biomarkers. For the continuous immunologic outcomes, we will calculate means by sampling time and perform exploratory graphical analyses, but with the small sample sizes and potentially irregular lengths of the series of observations it will not be possible to perform formal longitudinal analysis. We will apply non-parametric tests to evaluate changes in immunologic outcomes before and after BCI. Details are provided below.

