10.4.4 Analysis of the Secondary Endpoint(s)

Wilcoxon signed-rank tests will be used to assess paired pre- and post-BCI peripheral blood measurements, and to assess paired post-BCI peripheral blood CD8⁺ T cell responses and T cell PD-1 expression in BAL effluent.

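### The 770-gene panel has no multiplicity control: tested gene by gene at the stated 0.05 level, about 38 genes per comparison would be called significant if BCI had no effect

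*Combined protocol and SAP*

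**What the plan says.** Section 10.4.1 states that P "values will be considered statistically significant at the 0.05 level". It adds that the study is not powered for the secondary outcomes, but says nothing about adjusting for the number of tests. Section 10.1 says "We will apply non-parametric tests to evaluate changes in immunologic outcomes before and after BCI", and Section 10.4.4 names the method: "Wilcoxon signed-rank tests will be used to assess paired pre- and post-BCI peripheral blood measurements".

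The gene panel falls within that scope. The Protocol Summary lists change in lymphocyte gene expression among the secondary endpoints. Section 3.2 says "We also hypothesize that there will be significant changes in peripheral blood lymphocyte gene expression after BCI", to be assessed with "a 770-plex gene expression panel covering innate and adaptive immune responses". Section 4.2.2 describes the panel again as one "which measures 770 gene targets most relevant in tumor immunobiology". It plans RNA quantitation in two sorted populations, CD8+ and CD4+CD25- cells, and picks out nine genes of particular interest with an open-ended list. Section 7.1.1 gives the sampling times: "Blood draws on day 0 (prior to BCI) and on days 7 and 14".

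Nowhere does the plan give a family-wise or false discovery rate correction, a testing hierarchy, a closed gene list, or a rule for when the gene-expression hypothesis counts as supported.

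**The concern.** A 0.05 threshold limits false positives for one test. Used separately on hundreds of genes, it produces a list of nominally significant genes whether or not BCI does anything, and a reader of that list cannot tell signal from chance.

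Section 10.5 says the trial's results will be critical for designing later studies of BCI combined with anti-PD-1 therapy. The gene panel is part of those results, so chance findings could be carried forward as candidate biomarkers of a BCI effect.

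**Working it through.** **Inputs.** Per-test level 0.05 (10.4.1). Paired signed-rank test (10.4.4). 770 genes (3.2, 4.2.2). Two sorted cell populations (4.2.2). Two post-BCI draws, days 7 and 14 (7.1.1). N = 15, a difference of 0.75 SD and within-subject correlation 0.5 (10.5). The plan does not state sidedness; two-sided is assumed.

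**1. The plan's own power figure.** Section 10.5 gives about 80% power at N = 15.
- SD of the difference = SD × √(2 × (1 − 0.5)) = 1.0 SD, so the standardised difference is 0.75.
- Normal approximation: Φ(0.75 × √15 − 1.96) = Φ(0.945) = 82.8%.
- Paired t: 77.1%. Signed-rank test by simulation: 75.0%.

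The figure is reproduced as an approximation. It is the power of one test at 0.05 and makes no allowance for multiple tests.

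**2. Expected false positives if BCI has no effect and each gene is tested.**
- One population at one draw: 770 × 0.05 = 38.5. The signed-rank test is discrete; its exact level at n = 15 is 0.0479, which gives 36.9.
- Both populations at both draws: 770 × 2 × 2 = 3,080 tests, and 3,080 × 0.05 = 154.

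**3. Chance of at least one false positive in a single comparison.**
- Independent genes: 1 − 0.95^770, with 0.95^770 = 7.0 × 10⁻¹⁸, so effectively 1.
- Correlated genes (assumed structures, n = 15, 1,000 simulated trials each):

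| Structure | P(at least one) | Mean count |
|---|---|---|
| One common factor, ρ = 0.3 | 1.00 | 37.6 |
| One common factor, ρ = 0.5 | 0.99 | 37.8 |
| One common factor, ρ = 0.8 | 0.63 | 32.7 |
| 20 gene blocks, ρ = 0.5 | 1.00 | 37.2 |
| 20 gene blocks, ρ = 0.8 | 1.00 | 36.8 |
| 20 gene blocks, ρ = 0.9 | 0.99 | 35.9 |

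Correlation changes how the false positives cluster but leaves their average number at about 33 to 38.

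**4. The narrowest reading: only the nine named genes (independence assumed).**
- One comparison: 9 × 0.05 = 0.45 expected; 1 − 0.95^9 = 37%.
- All four comparisons: 36 × 0.05 = 1.8 expected; 1 − 0.95^36 = 84%.

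**5. Is correction attainable at this size?** The smallest two-sided signed-rank p is 2/2ⁿ. The first Benjamini-Hochberg step at 5% over 770 genes is 0.05/770 = 6.49 × 10⁻⁵, and k genes sharing the minimum p pass if that p is at most k × 6.49 × 10⁻⁵.
- n = 15: minimum p 6.10 × 10⁻⁵, so one gene can pass alone.
- n = 14: 1.22 × 10⁻⁴ ÷ 6.49 × 10⁻⁵ = 1.9, so at least 2 genes must reach the minimum.
- n = 12: 4.88 × 10⁻⁴ ÷ 6.49 × 10⁻⁵ = 7.5, so at least 8.

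If the family is all 3,080 tests, the first step is 0.05/3,080 = 1.62 × 10⁻⁵. At n = 15, 6.10 × 10⁻⁵ ÷ 1.62 × 10⁻⁵ = 3.8, so at least 4 tests must reach the minimum together.

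**The case against.** The best defence is that this is a phase I study whose secondary outcomes are openly unpowered, that the panel work is described as preliminary, and that interest centres on a few key genes. Each part has limits. Lack of power concerns missed effects; it does not lower the false-positive count, and with fewer true effects detected a larger share of the listed genes is false. Section 10.1 calls only the graphical analyses exploratory, and the panel sits among the secondary endpoints rather than in the exploratory Section 4.2.3. The nine genes are examples, not a closed list, and testing only those nine would still leave a 37% family-wise error per comparison. The narrower reading does, however, give far fewer false positives than 38.5, and the plan should say which reading it intends.

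A reader might infer that every test in the trial is uncontrolled. The documents do not support that. Feasibility is an estimate with an exact confidence interval (10.4.2), safety is descriptive and the MTD follows from 3+3 counts (10.4.3, 6.1.2). In the dose-level subgroup tests (10.4.7), three pairs cannot give a two-sided p below 2/2³ = 0.25.

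A reader might also infer that chance alone would confirm the gene-expression hypothesis. The plan has no rule for confirming it, and Section 10.2, the list of statistical hypotheses, omits it. Per-gene testing is the plain reading of 10.1 and 10.4.4 but is not spelled out.

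Finally, correction is tight at this size. Fewer than 15 complete pairs is plausible: Section 5.6 gives 15–24 participants, those found not to have NSCLC give no post-BCI blood (7.1.2), and samples are discarded for those who withdraw after the post-BCI draws (5.7.2). That is a real cost, but it does not make the unadjusted list interpretable. Presenting the panel as hypothesis-generating with no significance claims would also be defensible, but 10.4.1 and 3.2 currently do the opposite.

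**Conclusion.** The concern holds for the gene panel. If each gene is tested at the stated 0.05 level and BCI has no effect, about 38 genes per comparison are expected to be called significant. The figure of 154 applies only if both populations and both draws are tested, which the plan implies but does not state as an analysis. At least one false positive is near-certain under independence or moderate correlation. The lowest probability found was 0.63, with an assumed correlation of 0.8 across all 770 genes.

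These results rest on per-gene testing, two-sided tests and no true change. Safety, MTD and feasibility conclusions do not depend on the panel. The point does not extend to a claim that all tests are affected or that the hypothesis would be confirmed, and it does not require 0.05 to be reserved for a single lead immune test.

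**What to change.** In Sections 10.4.1 and 10.4.4, state that significance on the gene panel is declared by the Benjamini-Hochberg procedure at a pre-stated false discovery rate, for example 5% or 10%. State the family: each cell population and draw separately, or all four together. Control within each of four families does not control error across them, so the choice should be explicit. Report raw and adjusted p-values.

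The cost is a few sentences and a line of code, with no added patients or samples. Fewer genes will be called significant. With 770-gene families at 5%, no gene can pass alone with fewer than 15 complete pairs; at least 2 must reach the minimum p at n = 14, and 8 at n = 12. Bonferroni would be harsher: at 0.05/770, paired-t power for a 0.75 SD change is 3.4% at n = 15 and 17.7% at n = 24.
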